## ABSTRACT

Third molar extraction is a common oral surgical procedure often associated with postoperative pain, edema, and functional limitation. Effective postoperative management plays a key role in minimizing morbidity and promoting patient comfort. Strategies such as cryotherapy may contribute to improved recovery and quality of life after surgery. **Objective:** to investigate the effects of cryotherapy on postoperative outcomes (pain intensity, edema, trismus and quality of life) following mandibular third molar extraction. **Materials and Methods:** This study was designed as a randomized split-mouth clinical trial. The sample consisted of 17 patients (34 mandibular third molars with equivalent levels of impaction) who underwent bilateral surgical extraction. The surgical sites were allocated into two groups according to postoperative care: Group A (control side—without cryotherapy) and Group B (test side—with postoperative cryotherapy using ice packs). All intraoperative and postoperative procedures, instructions, and medications were identical for both groups. Patients were evaluated for pain intensity, trismus severity, presence of edema, and quality of life for up to seven days postoperatively (D7). The evaluator was aware of the postoperative intervention applied. Repeated-measures ANOVA was used to analyze each outcome variable, and associations between continuous variables were assessed using Pearson's correlation test. Statistical significance was set at 5% ( $P < 0.05$ ). **Results:** Overall, postoperative pain intensity was lower in patients who received cryotherapy. Group A reported significantly higher pain intensity on postoperative days 1 and 3. No signs of trismus were observed in Group B at the end of the follow-up period, whereas Group A presented restricted mouth opening at D7. Both groups exhibited edema on postoperative day 2 (D2); however, complete regression of edema by D7 was observed only in Group B. Additionally, a significant association between pain intensity and trismus severity was identified in Group A at D7. Quality-of-life assessment revealed significant differences in three questionnaire items favoring Group B, including greater perceived improvement, better mouth opening, and reduced difficulty sleeping. **Conclusion:** The findings suggest that postoperative cryotherapy is effective in reducing pain intensity and trismus following mandibular third molar extraction. Moreover, this physical therapy modality appears to enhance pain tolerance and patients' self-perceived healing.

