#### **4.4 SAMPLE**

The sample selection consisted on patients referred to the Federal University of Rio Grande do Sul's Dentistry School. The selected patients require bilateral extraction of lower third molars under local anesthesia in two different surgical times. There will be no change to the routine care for patients volunteering in the study. The surgical procedures will be performed by the research team responsible for this study. Participants of both sexes, aged 18 to 50 years, were included in the study if they presented an indication for bilateral surgical removal of mandibular third molars in similar positions according to Pell and Gregory classification. Additional inclusion criteria comprised the absence of systemic comorbidities, local conditions free of inflammatory or infectious processes, no history of allergy to the prescribed medications, and no recent or chronic use of antibiotics, anti-inflammatory drugs, corticosteroids, or analgesics. Participants were excluded from the study if they used medications other than those prescribed by the surgeon, failed to provide the required data, belonged to Group A (control) but used postoperative ice packs, or belonged to Group B (test) and did not use ice packs as instructed by the researchers. There were three dropouts due to noncompliance with postoperative recommendations and the use of non-prescribed medication, resulting in 34 procedures performed in 17 patients.

Postoperative consultations were conducted for follow-up, suture removal, and the evaluation and treatment of any potential postoperative complications.

The selection of the control group and experimental groups were determined by a simple randomization in the immediate postoperative period. One surgical site didn't receive cryotherapy (GA), while the other site received cryotherapy with ice (GB).

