#### **4.6 POSTOPERATIVE CARE**

In the immediate postoperative period following the first surgical procedure, the allocation of postoperative care—with or without cryotherapy—was randomized using a simple draw. Allocation was determined by the selection of a folded paper indicating Group A or Group B and was supervised by a third party to ensure allocation concealment. When the first surgical site of a patient was assigned to Group A (control), the contralateral site in the second surgical procedure was assigned to Group B (test), and vice versa.

Group A (control) did not receive postoperative cryotherapy. Group B (test) was instructed to apply standardized ice packs (11 × 8.5 × 1 cm), provided by the research team, positioned diagonally to cover both the mandibular angle and the cheek on the operated side. Cryotherapy was initiated immediately after surgery under surgeon supervision and continued for the first 12 postoperative hours, consisting of 30-minute applications followed by 30-minute intervals (total of 12 applications). During the intervals, patients were instructed to store the ice packs in a freezer until the next application.

All participants received identical pharmacological postoperative instructions (APPENDIX B) for both interventions, including paracetamol 1 g every 6 hours for 3 days and mouth rinses with 0.12% aqueous chlorhexidine digluconate twice daily for 7 days, starting on the day following surgery. In cases of persistent pain, trismus, or edema that significantly interfered with daily activities despite the use of prescribed analgesics, patients were instructed to use rescue medication consisting of codeine 30 mg every 4 hours as needed.

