#### 4.8 STATISTICAL ANALYSIS

Data normality was assessed using the Kolmogorov–Smirnov test. Parametric analyses were applied to compare groups (control side vs. test side) and postoperative time points (from day 0 to day 7). Continuous variables, including pain intensity (VAS scores), maximum mouth opening (mm), and facial edema (mm), were expressed as means  $\pm$  standard deviation (SD).

A two-way repeated-measures analysis of variance (ANOVA), followed by Fisher's least significant difference (LSD) post hoc test, was used to evaluate the main effects of time and treatment, as well as their interaction, for pain intensity, trismus, and edema. Pain reports were also qualitatively analyzed based on the frequency distribution of pain categories (no pain, mild pain, moderate pain, and severe pain) for both groups.

Associations between pain intensity and trismus or edema were assessed using Pearson's correlation coefficient. Trismus and edema were additionally evaluated using the formulas (Baseline – Postoperative) and (Postoperative – Baseline), respectively. Qualitative data related to quality of life were presented as percentages.

All statistical analyses were performed using SPSS software (version 20.0; IBM Corp., Armonk, NY, USA). Statistical significance was set at  $P < 0.05$ .

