### 5 RESULTS

#### 5.1 POSTOPERATIVE PAIN INTENSITY

The analysis demonstrated significant main effects of treatment ( $F_{(1,16)} = 5.063$ ,  $p = 0.039$ ) and time ( $F_{(7,112)} = 6.254$ ,  $p < 0.001$ ) on postoperative pain intensity (Table 1). Overall, pain scores were higher in Group A than in Group B ( $2.0 \pm 1.2$  vs.  $1.3 \pm 1.1$ ;  $F_{(1,16)} = 5.063$ ,  $p = 0.039$ ).

[figure not shown]

[figure not shown]
Table 1: Average pain levels on every post-operative day for each group. (\*) indicates statistical differences between control and test groups.

In Group A, pain intensity was significantly higher on postoperative days 1 ( $3.59 \pm 0.59$ ;  $p = 0.014$ ) and 3 ( $3.24 \pm 0.55$ ;  $p = 0.005$ ) compared with day 0 ( $1.35 \pm 0.54$ ). No significant differences were observed between day 0 and the remaining postoperative time points ( $p > 0.05$ ).

[figure not shown]
On the test side (Group B), no significant differences in pain intensity were observed between day 0 and any postoperative evaluation ( $p > 0.05$ ), suggesting that cryotherapy effectively prevented postoperative pain exacerbation.

A significant interaction between treatment and time was also observed ( $F_{(7,112)} = 2.689$ ,  $p = 0.013$ ). Pain intensity was higher on postoperative day 1 (Group A:  $3.59 \pm 0.59$  vs. Group B:  $2.12 \pm 0.42$ ;  $p = 0.017$ ) and day 3 (Group A:  $3.24 \pm 0.55$  vs. Group B:  $1.29 \pm 0.33$ ;  $p = 0.007$ ) in the control group compared with the cryotherapy group.

Postoperative pain was absent in 29.4% of control cases and 44.1% of cryotherapy cases. Mild pain was reported by 50.0% of participants in Group A and 47.8% in Group B, whereas moderate pain occurred in 16.9% and 7.4% of cases, respectively. Severe pain was reported by 3.7% of control cases and 0.7% of cryotherapy cases (Graphics 1 and 2).

Graphic 1: Prevalence of reports of moderate to severe pain (4-10 in visual analogic scale) in the total number of reports of pain (1-10 in visual analogic scale) in the control group after day 2 (last day of analgesic medication).

12

Graphic 2: Prevalence of reports of moderate to severe pain (4-10 in visual analogic scale) in the total number of reports of pain (1-10 in visual analogic scale) in the test group after day 2 (last day of analgesic medication).

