## 5.4 QUALITY OF LIFE

Among the 14 items of the OHIP-14 questionnaire, only three showed significant differences between groups. Regarding mouth opening, 31% of participants in Group A still reported difficulty opening the mouth on postoperative day 7, compared with 23.5% in Group B. Concerning sleep disturbances, Group A showed an approximate 40% reduction in complaints between postoperative days 2 and 7, whereas Group B demonstrated a reduction of approximately 66.6%.

When participants were asked which intervention resulted in greater postoperative improvement, all patients who underwent the control protocol in the first surgery (100%) preferred the cryotherapy intervention. Among those who received cryotherapy during the first procedure, 83% also indicated preference for the cryotherapy side.

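### The pain ANOVA has no surgery-order term; with an 11:6 split of orders, the overall pain difference carries 5/17 of any first-versus-second-surgery difference, whose size and sign are not reported

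*Combined protocol and SAP*

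**What the plan says.** - **Design.** Section 4.4 selects patients who need "bilateral extraction of lower third molars under local anesthesia in two different surgical times". Section 4.6 describes a simple draw after the first operation to set its care. If that is control, "the contralateral site in the second surgical procedure was assigned to Group B (test), and vice versa". No blocking of the order is described.
- **Model.** Section 4.8 plans a two-way repeated-measures ANOVA that "was used to evaluate the main effects of time and treatment, as well as their interaction, for pain intensity, trismus, and edema". Time there means postoperative day 0 to 7, not first or second operation. Order, period and sequence are not mentioned.
- **Numbers.** Section 4.4 reports three dropouts, "resulting in 34 procedures performed in 17 patients". The Discussion (section 6) puts 11 participants in the control-first group. Section 5.4 adds: "Among those who received cryotherapy during the first procedure, 83% also indicated preference for the cryotherapy side".
- **Result.** Section 5.1 states "Overall, pain scores were higher in Group A than in Group B": 2.0 vs 1.3, F(1,16) = 5.063, p = 0.039. The abstract opens its results with the same finding: "Overall, postoperative pain intensity was lower in patients who received cryotherapy". Section 5.1 also says "A significant interaction between treatment and time was also observed" (p = 0.013). Pain is not reported by surgery order.

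**The concern.** Within each patient, treatment is tied to surgery order. If pain differs between a first and a second operation for reasons unrelated to ice, that difference cancels from the group comparison only when the two orders are equally frequent. Here they are not, and the model does not remove what is left. The error degrees of freedom agree: 17 patients with no sequence factor leave 16, whereas a sequence factor would leave 15.

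At stake are the size and precision of the overall pain effect, which is the first result in the abstract and has p close to 0.05. A reader cannot tell what part of the 0.7 points, if any, belongs to surgery order. The order was recorded, since preference is reported by it.

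**Working it through.** **Inputs.** Mean pain 2.0 and 1.3, F(1,16) = 5.063 and p = 0.039; day 1 means 3.59 vs 2.12 (p = 0.017) and day 3 means 3.24 vs 1.29 (p = 0.007), all from section 5.1. 17 patients (section 4.4). 11 control-first (section 6).

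**Split.** 17 - 11 = 6 cryotherapy-first. The 83% in section 5.4 fits 5/6 = 83.3%. Had the 11 been counted among 20 enrolled, 9 would remain, and 7/9 = 78% and 8/9 = 89% do not fit.

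**Reported p-value.** The upper tail of F(1,16) at 5.063 is 0.0389, which reproduces 0.039.

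**Order share.** Let tau be the A-minus-B effect and pi the first-minus-second-surgery difference. The expected A-B difference is tau + pi in control-first patients and tau - pi in cryotherapy-first patients. The mean over 17 is tau + pi(11 - 6)/17 = tau + (5/17)pi = tau + 0.294 pi.

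**Spread implied by the reported figures.** t = sqrt(5.063) = 2.250. SE = 0.7/2.250 = 0.311. SD of paired differences = 0.311 x sqrt(17) = 1.283. Total SS = 16 x 1.283^2 = 26.32.

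**Order-adjusted test.** The adjusted estimate is 0.7 - (5/17)pi, with pi now the observed order difference.
- Order SS = 4 x (11 x 6/17) x pi^2 = 15.53 pi^2.
- Residual SS = 26.32 - 15.53 pi^2, on 15 df.
- SE = sqrt(residual SS/15) x 0.5 x sqrt(1/11 + 1/6).

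| Observed pi (first minus second) | Adjusted A-B | SE | p (15 df) |
|---|---|---|---|
| 0 | 0.70 (95% CI -0.02 to 1.42) | 0.336 | 0.055 |
| +0.5 | 0.55 | 0.310 | 0.095 |
| -0.5 | 0.85 | 0.310 | 0.016 |

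The 0.5 values are illustrative; the documents give none. Over all possible values of pi, the largest p is 0.102.

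**Bound on the point estimate.** Residual SS reaches zero at |pi| = sqrt(26.32/15.53) = 1.302. The order share is then at most 5/17 x 1.302 = 0.383, and the adjusted estimate at least 0.7 - 0.383 = 0.317. For a difference between 0.6 and 0.8, the range that rounding allows, this minimum is 0.27 to 0.36. The bound applies to the observed order contrast, not to the true order effect.

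**Error rate of the unadjusted test.** In simulations of 17 pairs with SD 1.28 and no treatment effect, the unadjusted 5% test rejects about 5% of the time under a fair draw. Held at exactly 11:6, it rejects about 5.5% of the time for an order difference of 0.5 points and about 6% for 1.0 point.

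**Other pain results.** The treatment-by-day interaction and changes from day 0 are unaffected by an order difference that is constant across days. The day 1 difference (3.59 - 2.12 = 1.47) and the day 3 difference (3.24 - 1.29 = 1.95) carry the same 5/17 share. If they were paired tests on 16 df, their adjusted p-values are 0.026 and 0.012 at zero order difference. They are at most 0.046 and 0.020 at any possible order difference, allowing for rounding of the reported p-values.

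**The case against.** The strongest reply is that order was randomised. Over repeated draws any order difference averages out of the estimate and adds to the variance that the paired SE already contains, so the reported test is valid. A split of 11:6 or more uneven has probability 0.33 under a fair draw, so nothing suggests a faulty draw. This stands, with one condition: these statements treat the 17 as the randomised set. Section 4.1 gives 20 patients, three were dropped after allocation, and their order is not stated. Exclusion must be assumed unrelated to order.

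It is also fair to say that the p-value of 0.055 is weak evidence of anything. It arises with the estimate unchanged at 0.70, from a wider SE and one lost degree of freedom. With the residual variance held at its unadjusted value, p would be 0.048. This stands too, and crossing 0.05 should not be the criterion.

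A reader might go further and infer that an order effect produced the benefit, or that p = 0.039 is wrong. The documents support neither: pain is not reported by order, and the sign of any order difference is open. Nor do they support the opposite inference, that the direction of effect is beyond doubt. Only the sign of the point estimate is fixed by the reported figures; the adjusted interval can include zero.

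What remains after these replies is that, for the split actually obtained, the estimate includes a known fraction of an unreported quantity that the trial's own data could remove.

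**Conclusion.** The point holds as one of conditional bias and precision, not of an invalid test. Given 11:6, the overall pain difference of 0.7 includes 5/17 of any first-minus-second-surgery difference, in either direction. The adjusted point estimate stays positive, at about 0.27 or more allowing for rounding, for every observed order difference compatible with the reported figures. The interaction result, and the day 1 and day 3 contrasts under the conditions stated with them, are not threatened.

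This rests on an additive order difference equal in both sequences, no carry-over, and the 6 obtained by subtraction. The adjusted p-values are scenarios; the actual one needs the patient-level data. This is a worthwhile, inexpensive improvement rather than a correction of an error.

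**What to change.** Keep the planned ANOVA and report an order-adjusted analysis of overall pain beside it.

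- Take the mean A-B difference within each sequence (control-first, cryotherapy-first), average the two with equal weight, and test on 15 df.
- If this is fitted as a model with sequence as a between-patient factor, use equally weighted sequence means. The order effect is then the treatment-by-sequence term, not the sequence main effect.
- Report the adjusted A-B difference and the order effect, each with its 95% CI, and state the 11:6 split.
- Do the same for the day 1 and day 3 between-group contrasts.
- Judge the outcome by how far the estimate and its interval move. If the adjusted difference stays near 0.7, a p-value just above 0.05 reflects the price of adjustment and is not evidence of bias.

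No new data are needed. The cost is one error degree of freedom (16 to 15). If the observed order difference is zero, the SE is also about 8% wider: sqrt(289/264) = 1.046 for the uneven split, times sqrt(16/15) = 1.033 for the lost degree of freedom, gives 1.081.

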## 4.7 STUDY VARIABLES

The outcome variables of this study were postoperative pain, trismus, local edema, and changes in quality of life following mandibular third molar extraction. Postoperative assessments were performed by the research team, consisting of two calibrated surgeons and one supervising professor, on postoperative days 0 (day of surgery), 2, and 7. The following evaluation protocols were applied:

a) Pain assessment: postoperative pain was assessed using a visual analog scale (VAS– APPENDIX C) ranging from 0 to 10, in which 0 represented no pain, 1–3 mild pain, 3.1–6 moderate pain, and 6.1–10 severe pain. Patients completed the scale at home daily until postoperative day 7.

b) Trismus assessment: trismus was evaluated by measuring maximum mouth opening with the patient seated and the tragus–ala plane parallel to the ground. Patients were instructed to open their mouths three consecutive times, and the mean value was recorded. Measurements were obtained as the interincisal distance in millimeters using a measuring tape. In the absence of maxillary or mandibular incisors, the occlusal edges were used as reference points. Measurements were recorded on postoperative days 0, 2, and 7.

c) Edema assessment: facial edema was measured using the method described by Gabka and Matsumura. Three linear facial measurements were obtained in millimeters with a measuring tape: tragus to pogonion, tragus to oral commissure, and lateral canthus to mandibular angle. The mean of these three measurements was calculated to quantify edema. This assessment was performed preoperatively and on postoperative days 2 and 7.

d) Quality of life assessment: quality of life was evaluated using a questionnaire adapted from the OHIP-14 (APPENDIX D), consisting of 14 dichotomous (yes/no) questions addressing daily functional limitations. The questionnaire included items related to chewing and swallowing ability, dietary changes, alterations in taste, mouth opening, voice changes, speech intelligibility, facial appearance, sleep disturbances, and ability to perform work-related activities. The questionnaire was provided to participants on the day of surgery and completed on postoperative days 0, 2, and 7. At the conclusion of the evaluation period following the second intervention, participants also answered the question: “Which intervention did you perceive as resulting in greater postoperative improvement?”

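### No primary outcome and no multiplicity rule: six treatment-related F tests each run at 5%, so the efficacy wording for pain and mouth opening is not error-controlled

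*Combined protocol and SAP*

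**What the plan says.** Section 4.7 introduces the endpoints without ranking them: "The outcome variables of this study were postoperative pain, trismus, local edema, and changes in quality of life". The general objective in section 2.1 likewise names all four together.

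Section 4.8 specifies a two-way repeated-measures ANOVA, "followed by Fisher's least significant difference (LSD) post hoc test", and says that it is "used to evaluate the main effects of time and treatment, as well as their interaction, for pain intensity, trismus, and edema". The significance level is 0.05 throughout. No hierarchy, gatekeeping or adjustment across outcomes or across the two treatment-related terms is stated. Quality of life is handled differently: "Qualitative data related to quality of life were presented as percentages".

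The abstract then concludes that "postoperative cryotherapy is effective in reducing pain intensity and trismus". Section 7 makes the same claim for pain and adds that cryotherapy shortened the time for which mouth opening was limited. It reports no significant effect on edema.

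**The concern.** With no primary outcome and no rule for combining tests, a benefit can be claimed from either the treatment effect or the interaction, for any of three outcomes. The results were read in that way. For pain, both tests are cited. For mouth opening, section 5.2 reports no treatment effect (p = 0.93), and the only between-treatment F test behind the claimed benefit is the interaction (p = 0.016).

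What is at stake is whether the statements on pain and mouth opening can be presented as confirmed findings. The issue concerns the omnibus F tests across outcomes. It would remain even if the unadjusted daily LSD comparisons were corrected, because the protection that the omnibus F gives to LSD works within one ANOVA and not across outcomes.

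**Working it through.** **Inputs.** F statistics and degrees of freedom come from sections 5.1 (pain), 5.2 (mouth opening) and 5.3 (edema). The three time main effects are left out because they do not compare treatments.

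**Step 1: reproduce the printed p-values** as the upper tail of the F distribution.

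| Test | F (df) | Printed p | Recomputed p |
|---|---|---|---|
| Pain, treatment by time | 2.689 (7,112) | 0.013 | 0.0130 |
| Mouth opening, treatment by time | 4.703 (2,32) | 0.016 | 0.0162 |
| Pain, treatment | 5.063 (1,16) | 0.039 | 0.0389 |
| Edema, treatment by time | 1.533 (2,32) | 0.23 | 0.231 |
| Edema, treatment | 0.516 (1,16) | 0.48 | 0.483 |
| Mouth opening, treatment | 0.006 (1,16) | 0.93 | 0.939 |

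All six reproduce. The last appears truncated rather than rounded, which is immaterial.

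**Step 2: error rate with no adjustment.** With six independent true nulls, the chance of at least one p below 0.05 is 1 − 0.95^6 = 0.265. Under any dependence it is at most 6 × 0.05 = 0.30.

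**Step 3: Holm over the six tests** (recomputed p-values; multiply the smallest by 6, the next by 5, and so on, never letting an adjusted value fall below the one before it).

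- Pain interaction: 6 × 0.0130 = 0.078
- Mouth-opening interaction: 5 × 0.0162 = 0.081
- Pain treatment: 4 × 0.03887 = 0.155

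The other three are 0.69 or higher. Using the printed p-values gives 0.078, 0.080 and 0.156. The Bonferroni threshold is 0.05/6 = 0.0083, against a smallest p of 0.013. Hochberg gives the same three values as Holm, and Hommel gives 0.065, 0.081 and 0.155. None reaches 0.05.

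**Step 4: sensitivity to the family** (Holm within each).

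| Family | Pain | Mouth opening |
|---|---|---|
| Three interactions | 3 × 0.0130 = 0.039 | 2 × 0.0162 = 0.032, raised to 0.039 |
| Three main effects | 3 × 0.0389 = 0.117 | 0.966 |
| Each outcome's own two tests | interaction 2 × 0.0130 = 0.026; treatment 0.039 | interaction 2 × 0.0162 = 0.032 |
| Pain treatment plus the mouth-opening and edema interactions | 2 × 0.0389 = 0.078 | 3 × 0.0162 = 0.049 |
| Pain treatment as a single pre-named test | 0.039 | not tested |

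The answer for pain and for mouth opening changes with the family chosen, and the plan chooses none.

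**The case against.** The strongest reply is that the six-test family is itself a choice made after the fact. Section 5.2 treats day 0 as baseline for mouth opening, and edema is also measured preoperatively. For these two outcomes the treatment main effect averages in a pre-treatment value, and the interaction is the natural test of differential change. On that view the three interactions are the relevant family, and pain and mouth opening both pass. This stands as a reason not to say that nothing survives correction. It does not rescue the claims, because section 4.8 tests main effects and interactions alike and nominates neither. A family picked once the results are known does not control error.

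Second, the observed pattern is not one stray result. Three of six tests are below 0.05, which has probability of about 0.2% under six independent true nulls. The Simes test of the global null gives 6 × 0.0162 / 2 = 0.049. This too stands, and it counts against reading the data as no effect on anything. It does not say which outcome is affected, and the abstract and section 7 make outcome-specific claims.

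Third, the sample size in section 4.1 derives from a pain-perception study, so a reader might infer that pain was primary. The section never says so, and it gives no effect size for this trial.

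Fourth, the abstract introduces its conclusion as something the findings suggest, and edema is openly reported as negative. That is fair, but section 7 carries no such hedge.

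Fifth, the mouth-opening claim has another weakness that Holm does not address: the day-0 means differ (43.8 against 39.3 mm). That is a separate matter.

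**Conclusion.** The concern holds in a limited form. No primary outcome or multiplicity rule is stated, and over the full set of six treatment-related F tests in section 4.8 no Holm-adjusted p-value reaches 0.05 (0.078, 0.081 and 0.155 for the three smallest). Some smaller families would pass and others would not. Since none was fixed in advance, the efficacy wording is not error-controlled. Mouth opening has the narrower support, with a null treatment main effect and the interaction alone behind the claim.

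Two stronger readings are not supported. A reader might infer that no result survives any family-wise correction; the three interactions, and the families within each outcome, do survive. A reader might also infer that cryotherapy does not work; adjusted values just above 0.05 in 17 patients do not show that.

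The figures take the printed F statistics and degrees of freedom at face value. The 26.5% error rate assumes independence, and the 30% bound does not.

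**What to change.** In section 4.8, state that no primary outcome was pre-specified. If a document dated before the results (for example the ethics submission) names one, cite it, test that outcome at 5% and treat the rest as secondary. Naming a primary now without such a document would be post hoc.

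Report Holm-adjusted p-values for the six tests beside the nominal ones, and state how the result changes with the family.

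Reword the efficacy statements in the abstract and section 7, for both pain and mouth opening, as exploratory. Keep the pain wording confirmatory only if a pre-results document names pain. For mouth opening, state that the treatment main effect was null (p = 0.93) and that the claim rests on the interaction alone.

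The cost is wording and one added column of p-values, with no new data. The downside is that the efficacy claims become weaker.
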